10.9. Appendix 9: Study Intervention Tolerability/Drop Comfort Assessment

The presence and severity of ocular symptoms will be elicited from the participant for their treated eye(s), as applicable. Symptoms including blurred vision, foreign body sensation, pain, burning/stinging, tearing, and itching will be classified using a 5-point grading scale with 0 = none, +0.5 = trace, +1 = mild, +2 = moderate, and +3 = severe. The duration of symptoms (< 1 minute, 1 to 5 minutes, > 5 minutes) will be captured once immediately after the drop of each dose of study intervention. If any other ocular symptoms are present, these will also be captured.

Participants will be asked to rate the overall comfort of the eye drops using a 6-point scale (i.e., soothing, very comfortable, comfortable, uncomfortable, very uncomfortable, or intolerable) immediately after the drop instillation for the right and left eyes separately, as applicable.

10.10. Appendix 10: Fundus (Indirect) Ophthalmoscope Examination

The fundus assessments should be conducted through a dilated pupil. The examinations will include evaluation of the lens, vitreous, fundus, and optic nerve. The cup to disc ratio will be assessed.

Lens

Lens Assessment: Use biomicroscopic examination, indirect lenses, direct/indirect ophthalmoscopy, etc., as appropriate, to visualize.

Lens Status: The lens will be evaluated for pathology. If pathology is present, it will be described.

Cataract Assessment: Under dilated ophthalmoscope examination, the presence and severity of nuclear, cortical and posterior subcapsular cataract lens opacities will be evaluated. At the first dilated ophthalmoscope examination, each type of cataract, if present, will be graded using the scale below. At the last follow-up dilated ophthalmoscope examination, each type of cataract will be assessed for change from baseline and if changed, the current severity will be graded using the scale below:

0	=	None
+1	=	Mild
+2	=	Moderate
+3	=	Severe

Vitreous

The vitreous will be evaluated for pathology. If pathology is present, it will be described. It will be noted if the condition is not evaluable.

Fundus

The fundus (posterior pole; periphery, when dilated) will be evaluated for pathology. If pathology is present, it will be described. It will be noted if the condition is not evaluable.

Optic Nerve

The optic nerve will be evaluated for pathology. If pathology is present, it will be described. It will be noted if the condition is not evaluable.

Cup/disc ratio will be reported using a 0.0 to 1.0 scale. It will be noted if the condition is not evaluable.

10.11. Appendix 11: IOP

[figure not shown]
IOP should be measured only after the biomicroscopic exam is completed and must be measured prior to pupil dilation. Measurements will be taken using a Goldmann applanation tonometer affixed to a slit lamp with the participant seated. The participant and slit lamp should be adjusted so that the participant's head is firmly positioned on the chin rest and against the forehead rest without leaning forward or straining. Tight fitting neckwear should be loosened. Both eyes will be tested, with the right eye preceding the left eye. The examiner looks through the binocular viewer of the slit lamp at low power. The tension knob is preset at a low pressure value (4 to 6 mm Hg). The examiner follows the image of the sodium fluorescein-stained semicircles while slowly rotating the tension knob until the inner borders of the sodium fluorescein rings touch each other at the midpoint of their pulsation in response to the cardiac cycle. When this image is reached, the examiner will take his/her fingers off the tension knob and record the IOP reading along with the date and time of day.

10.12. Appendix 12: Gonioscopy/Angle Assessment

Gonioscopy will be performed to assess the iridocorneal (anterior chamber) angle. For slit lamp gonioscopy, the assessor's preferred gonioscopy lens may be used. The room lights should be turned off during the examination and all participants should be examined in the same room with the same slit lamp and with consistent lighting conditions.

The assessor will begin by applying adequate topical anesthesia (topical proparacaine 0.5%) to the participant's eye. With the participant sitting comfortably at the slit lamp, the corneal surface of the lens will be wetted with an artificial tear or lubricating solution and the gonioscopy lens will be placed on the participant's eye. A bright, narrow light beam will be directed away from the pupil to avoid inducing miosis and the angle assessment will be performed under high magnification. With the participant maintaining their gaze in the primary position, the assessor will examine/grade the 6 o'clock (inferior angle) position using the Shaffer anterior chamber angle grading system depicted in [Figure 10-2](#). Lens tilting should be minimized; only minor movement of the lens is permissible, otherwise, the angle findings may be distorted and a closed, or a narrow angle may appear open. Excess pressure should not be used as this may cause indentation; the presence of corneal striations is an indication that the cornea is being indented.

Figure 10-2 Anterior Chamber Angle Grading

Source: Becker and Shaffer. Clinical interpretation of gonioscopic findings. 8th ed. In: Stamper RL, Lieberman MF, Drake MV, editors. Becker-Shaffer's Diagnosis and Therapy of the Glaucomas. Amsterdam: Mosby Elsevier, 2009:78-90.

11. References

1.0 Introduction

This Statistical Analysis Plan (SAP) describes the statistical analyses for AGN-241622 Study 2011-101-013, A First-in-Human, Phase 1/2, Dose-ascending, Multicenter, Masked, Randomized, Vehicle-controlled Study Evaluating the Safety, Tolerability, and Pharmacokinetics of AGN-241622 in Healthy Subjects and Subjects with Presbyopia (Stage 1 and Stage 2) and Efficacy in Subjects with Presbyopia (Stage 2).

Due to Sponsor decision, the study was terminated after Stage 2a completion. This decision was not taken due to any safety reasons. The analysis described in this plan will be based on synoptic clinical study report (CSR).

The SAP will not be updated in case of administrative changes or amendments to the protocol unless the changes impact the analysis.

Unless noted otherwise, all analyses will be performed using SAS Version 9.4 (SAS Institute Inc., Cary, NC 27513) or later under the UNIX operating system. Pharmacokinetics analyses will be performed using Phoenix WinNonlin Version 8.3 or newer.

This SAP includes changes to analyses described in the protocol. Details are outlined in Section 12.1.

2.0 Study Objectives and Design

2.1 Study Objectives

The primary objective of this study is to evaluate the safety, tolerability, pharmacokinetics, and efficacy of AGN-241622 in healthy subjects and subjects with presbyopia.

2.2 Study Design Overview

Study 2011-101-013 is a Phase 1/2, multicenter, randomized, double-masked (except Cohort 7) study in healthy subjects and subjects with presbyopia. This study will be conducted in 3 stages (Stage 1, Stage 2a, and Stage 2b).

In Stage 1, the left eye will be the study eye and receive study treatment. In Stage 2a, both eyes will be study eyes and receive study treatment.

Study interventions by study stage and cohort are summarized in Table 1.

[figure not shown]
Table 1. Study Interventions by Study Stage and Cohort

Study Interventions by Study Stage and Cohort			
Stage 1	Single Ascending Doses in Healthy Subjects		
	Cohort 1	Cohort 2	Cohort 3
	AGN-241622 [REDACTED] single dose left eye 9 Active; 3 Vehicle	AGN-241622 [REDACTED] single dose left eye 9 Active; 3 Vehicle	AGN-241622 [REDACTED] single dose left eye 9 Active; 3 Vehicle
Stage 2a	Multiple Ascending Dose in Subjects with Presbyopia		
	Cohort 4	Cohort 5	Cohort 6
	AGN-241622 [REDACTED] Once daily (QD) x 14 days both eyes 9 Active; 3 Vehicle	AGN-241622 [REDACTED] QD x 14 days both eyes 9 Active; 3 Vehicle	AGN-241622 [REDACTED] QD x 14 days both eyes 9 Active; 3 Vehicle
Stage 2b*	Multiple-Dose Exploratory Cohorts in Participants with Presbyopia		
	Cohort 7	Cohort 8	
	AGN-241622 (dose strength to be determined [TBD]) versus pilocarpine HCl [REDACTED] 1.25% QD x 14 days both eyes 60 (30 per treatment arm)	AGN-241622 (dose strength TBD) (in participants who wear contact lenses) QD x 14 days both eyes 9 Active; 3 Vehicle	

* Stage 2b has not been conducted due to early discontinuation of the study after completion of Cohort 6.

The schematic of the study is shown in Figure 1.

Figure 1. Study Schematic

The data monitoring committee (DMC) will review available unmasked safety and plasma pharmacokinetic (PK) data, along with target engagement and efficacy data if necessary (and applicable), from each completed cohort to recommend if it is acceptable to proceed to the next planned cohort, modify the proposed dose strength (e.g., de-escalate to a lower dose strength), repeat the current dose strength, modify the cohort size, or stop the study. In addition, the Food and Drug Administration (FDA) will review study data after the completion of each cohort and the sponsor will wait until a positive response is received from the FDA to proceed to the next cohort.

2.3 Treatment Assignment and Blinding

All subjects will be centrally assigned to study intervention using an interactive web response system (IWRS). In each cohort for Cohorts 1 to 6 and 8, approximately 12 participants will be randomized in a 3:1 ratio to receive AGN-241622 ophthalmic solution or vehicle. Cohorts 1 to 6 and 8 will be double-masked. In Cohort 7, 60 participants will be assigned in a 1:1 ratio to receive pilocarpine HCl (██████████) 1.25% ophthalmic solution or AGN-241622 ophthalmic solution. Cohort 7 will be single masked, in which participants will be masked for the study intervention assignment and site staff and the investigator will not discuss the study intervention assignment with the participants.

2.4 Sample Size Determination

The sample sizes for each study stage were not determined based on statistical consideration.

The sample sizes for each cohort are expected to provide sufficient data to assess safety, PK parameters (as applicable), and efficacy (as applicable) of each dose of AGN-241622.

3.0 Endpoints

Efficacy assessments are conducted in Stage 2 (Cohort 4, 5, 6, 7, and 8) only.

3.1 Primary Endpoint(s)

The primary efficacy endpoint is the proportion of subjects gaining 3 lines or more from baseline in mesopic, high-contrast, binocular DCNVA at Day 14, Hour 3.

3.2 Other Efficacy Endpoint(s)

1. Proportion of participants gaining 2 lines or more in mesopic, high-contrast, binocular DCNVA
2. Change from baseline in mesopic, high-contrast, binocular DCNVA letters
3. Change from baseline in mesopic pupil diameter (mm) (distance and near)
4. Change from baseline in photopic pupil diameter (mm) (distance and near)
5. Change from baseline in photopic, high-contrast, binocular distance-corrected intermediate visual acuity (DCIVA) letters
6. Change from baseline in Near Vision Presbyopia Task-based Questionnaire (NVPTQ) (paper based) Performance score
7. Change from baseline in NVPTQ (paper based) Satisfaction score
8. Change from baseline in Presbyopia Impact and Coping Questionnaire (PICQ) Coping score

9. Change from baseline in PICQ Impact score

3.3 Safety Endpoint(s)

1. Adverse events (AEs)
2. Vital signs
3. 12-lead electrocardiogram (ECG)
4. Clinical laboratory assessments

3.4 Pharmacokinetic Endpoint(s)

Tear and plasma pharmacokinetic parameters.

3.5 Endpoint(s) to be analyzed for Synoptic CSR

Due to the early discontinuation of the Study after completion of Cohort 6, a synoptic CSR will be provided for this study, and only the endpoints 1 and 4 of Section 3.3 Safety Endpoints will be analyzed.

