2.2.1.3. Toxicology

Ocular and systemic toxicity of AGN-241622 was evaluated in rats, rabbits, and dogs. In the GLP-compliant rat toxicology study, male and female Sprague Dawley rats received daily dorsal subcutaneous injections of [REDACTED] mg/kg/day for 28 days. Marked reduced body weight growth and low food consumption were observed in animals administered \geq [REDACTED] mg/kg/day. However, tolerance to these effects gradually developed during the dosing phase, with robust recovery during the 2-week recovery phase. Consequently, the body weight and food consumption effects were considered nonadverse. However, due to the large difference in body

CONFIDENTIAL

AGN-241622

weight during the dosing phase, the dose of [REDACTED]/kg/day was considered minimally tolerated. Effects noted in clinical observations, functional observational battery, and clinical and anatomical pathology were related to expected pharmacology of an α 2-adrenergic receptor agonist, were reversible, and were considered nonadverse. For these reasons, the NOAEL for this study was [REDACTED]/kg/day and this dose has a [REDACTED] margin of safety over the predicted human exposure at the proposed starting clinical dose.

Respiratory function was assessed in male Sprague Dawley rats administered a single subcutaneous dose of [REDACTED] mg/kg AGN-241622. All dose levels of AGN-241622 lowered respiration rate (as much as -17%) and minute volume (as much as -26%), consistent with the expected pharmacologic activity of an α 2-adrenergic receptor agonist, with the primary effects occurring between approximately 1 and 3.5 hours postdose. The changes were not considered adverse and did not display strict dose dependency. However, because the effects observed in this study were present at all doses, they will still be monitored closely in this clinical study. The NOAEL for this study was the top dose of [REDACTED] mg/kg, providing a [REDACTED] margin of safety over the predicted human exposure at the proposed starting clinical dose.

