Stage 1	Primary	
 To evaluate the safety and tolerability of AGN-241622 administered once, unilaterally in healthy participants 	
 AEs Vital signs 12-lead ECG Clinical laboratory assessments Study intervention tolerability and drop comfort assessments IOP Slit lamp biomicroscopy
	Secondary	
 To evaluate the systemic and local pharmacokinetics of AGN-241622 administered once unilaterally in healthy participants To evaluate the target receptor engagement of AGN-241622 as compared with vehicle administered once, unilaterally in healthy participants 	
 Plasma and tear concentrations and PK parameters of AGN-241622, including but not limited to: $AUC_{0-\infty}$, AUC_{0-t}, C_{max}, T_{max}, $t_{1/2}$, CL/F (plasma only), and V_z/F (plasma only) Pupil diameter measurement (mesopic)
Stage 2a	Primary	
 To evaluate the safety and tolerability of AGN-241622 after repeat bilateral administration in participants with presbyopia 	
 AEs Vital signs 12-lead ECG Clinical laboratory assessments Study intervention tolerability and drop comfort assessments IOP Slit lamp biomicroscopy Contrast sensitivity Photopic and mesopic high contrast CDVA binocularly Manifest refraction (mesopic and photopic) Dilated funduscopic examination
	Secondary	
 To evaluate the systemic and local pharmacokinetics of AGN-241622 after repeat bilateral administration in participants with presbyopia 	
 Plasma and tear concentrations and PK parameters of AGN-241622, including but not limited to: $AUC_{0-\tau}$, AUC_{0-t}, C_{max}, T_{max}, $t_{1/2}$, CL/F (plasma only), and V_z/F (plasma only)

CONFIDENTIAL
AGN-241622

	Objectives	Measures
Stage 2a (Continued)	
 To evaluate efficacy of AGN-241622 compared with vehicle after repeat bilateral administration in participants with presbyopia 	
 Mesopic and photopic high contrast, binocular and monocular DCNVA Mesopic and photopic pupil diameter (distance and near) Depth of focus PRO Questionnaires (NVPTQ, PICQ, Single-item PGIC, Single-item PGIS) Bulbar conjunctival hyperemia

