9.4.2. Safety Analyses

The safety analyses will be performed using the safety population and will be fully defined in the SAP. The safety parameters will include AEs, vital signs, 12-lead ECG, and clinical laboratory assessments. Other safety parameters will be defined in the SAP.

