9.4.2.3. Vital Signs

For each stage, descriptive statistics for vital signs (systolic and diastolic blood pressure, heart rate, weight, respiration rate, and temperature) at baseline and changes from baseline at each postdose timepoint will be presented by study stage, cohort, and study intervention and by pooled vehicle in each stage.

Vital sign values will be considered to be PCS if they meet both the observed-value criteria and the change-from-baseline-value criteria that will be detailed in the SAP. Analysis will be detailed in the SAP.

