9.4.2.4. Electrocardiograms

For each stage, descriptive statistics for ECG parameters (heart rate, PR interval, QRS duration, QT interval, and QTc) at baseline, each postdose timepoint, and EOS; and changes from baseline at each postdose timepoint and at EOS will be presented by stage, cohort, and study intervention, and by pooled vehicle in each stage.

The criteria for PCS ECG values and analysis will be detailed in the SAP.

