9.4.2.5. Other Safety Analyses

All other safety endpoints will be analyzed with descriptive statistics. Detailed methods for the other safety endpoints will be described in the SAP.

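### Of the protocol's primary safety and tolerability measures for Stages 1 and 2a, the current SAP analyses only AEs and laboratory data (2 of 7 and 2 of 11), without a measure-level reason for dropping the rest

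*SAP*

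**What the plan says.** Protocol Section 3 gives these measures for the primary safety objective of Stage 1: "AEs Vital signs 12-lead ECG Clinical laboratory assessments Study intervention tolerability and drop comfort assessments IOP Slit lamp biomicroscopy". Stage 2a has the same seven and adds "Contrast sensitivity Photopic and mesopic high contrast CDVA binocularly Manifest refraction (mesopic and photopic) Dilated funduscopic examination".

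Protocol 9.4.2 reads: "The safety parameters will include AEs, vital signs, 12-lead ECG, and clinical laboratory assessments. Other safety parameters will be defined in the SAP". Sections 9.4.2.3 and 9.4.2.4 commit, for each stage, to descriptive statistics at baseline and for change from baseline in vital signs and ECG. They also expect criteria for potentially clinically significant (PCS) values in the SAP: "Vital sign values will be considered to be PCS if they meet both the observed-value criteria and the change-from-baseline-value criteria", and for ECG, "The criteria for PCS ECG values and analysis will be detailed in the SAP". Section 9.4.2.5 covers the remainder: "All other safety endpoints will be analyzed with descriptive statistics".

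The current SAP (version 3.0) lists four safety endpoints in Section 3.3: AEs, vital signs, ECG and laboratory assessments. Section 3.5 then says that, for the synoptic CSR, "only the endpoints 1 and 4 of Section 3.3 Safety Endpoints will be analyzed". Section 8 accordingly has AE and laboratory analyses only, and Appendix B has PCS criteria for laboratory parameters only.

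Two reasons are given. Table 3 in SAP 12.1 cites termination before Stage 2b and limits the work to key safety analysis, a term the SAP does not define. SAP 3.5 and the version history cite the move to a synoptic CSR. SAP 1.0 says that the study ended by sponsor decision after Stage 2a was complete, and not for safety reasons.

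**The concern.** Termination before Stage 2b explains why there are no Stage 2b outputs. It does not explain why measures of the primary objective from Stages 1 and 2a, which were conducted, are left out of the analysis. A synoptic CSR is a report format, and the SAP does not say why that format excludes one measure and keeps another.

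This is a first-in-human study, and AE tables do not replace the dropped summaries. Under protocol 10.3.1 an abnormal vital sign or ECG counts as an AE only when the investigator considers it clinically significant. A shift in mean heart rate, blood pressure, respiration rate or PR interval in which no single value reaches that threshold would appear in no planned output. Protocol 2.2.1.3 describes nonclinical effects in these domains: lower respiration rate in rats, and in dogs lower heart rate, PR longer by up to 13 msec and diastolic pressure higher by up to 10 mm Hg. The protocol treats these effects as nonadverse or as expected pharmacology. They show where a reader would look and are not evidence of harm in humans.

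The graded symptom scores and the 6-point drop comfort rating (protocol 8.2.5) also get no summary. Some tolerability will surface as ocular TEAEs, but the scales themselves will not be reported.

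**Working it through.** The plan states no power, alpha or precision figure on this point, so the check is a count, a comparison of the stated reasons, and a note on what the missing tables could show.

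**1. Count.** Measures are from protocol Section 3, listing from SAP 3.3, retention from SAP 3.5.

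| Measure | Stage 1 primary | Stage 2a primary | In current SAP 3.3 | Kept by SAP 3.5 |
|---|---|---|---|---|
| AEs | yes | yes | yes | yes |
| Laboratory | yes | yes | yes | yes |
| Vital signs | yes | yes | yes | no |
| 12-lead ECG | yes | yes | yes | no |
| Tolerability / drop comfort | yes | yes | no | no |
| IOP | yes | yes | no | no |
| Slit lamp | yes | yes | no | no |
| Contrast sensitivity | – | yes | no | no |
| CDVA | – | yes | no | no |
| Manifest refraction | – | yes | no | no |
| Dilated funduscopy | – | yes | no | no |

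- Stage 1: 7 measures, 2 kept (2/7 = 28.6%). The 5 missing are 2 listed and cut plus 3 not listed.
- Stage 2a: 11 measures, 2 kept (2/11 = 18.2%). The 9 missing are 2 listed and cut plus 7 not listed.

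**2. Reasons against omissions.**

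- Termination before Stage 2b concerns Cohorts 7 and 8. All the omissions above concern Cohorts 1 to 6.
- The synoptic format applies equally to every measure, so it cannot separate laboratory data (kept) from vital signs and ECG (cut).
- The same SAP keeps plasma and tear PK in Section 9. PK is a secondary objective in the protocol, so shortening the report did not fall on the secondary material first. The PK text also sits awkwardly with SAP 3.5 and with Table 3, which rules out outputs for other objectives and endpoints.

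**3. What the missing summaries could show.** The planned numbers are 9 per dose and 3 vehicle per cohort. SAP 4.0 pools vehicle within stage: 3 × 3 = 9. With s the SD of change from baseline, assumed equal across groups, and complete data, the 95% half-widths are:

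- Mean change within one dose: t(0.975, 8) / √9 = 2.306 / 3 = 0.77 s.
- Difference from pooled vehicle: t(0.975, 16) × √(1/9 + 1/9) = 2.120 × 0.471 = 1.00 s.

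The tables would therefore be descriptive. Their value is complete reporting of the primary objective, not a test.

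**The case against.** The sponsor's case has several sound parts. The reduction is open: SAP 1.0, 3.5, the version history and Table 3 all announce it. The protocol leaves the detail of safety analyses to the SAP. On the four parameters that protocol 9.4.2 names, the SAP keeps 2 of 4. Clinically significant findings still enter as AEs. The added tables are imprecise, and their volume exceeds a count of domains because each domain has several parameters and timepoints. Full tables for every ocular examination in a deliberately short report are a matter of judgement. These points limit the remedy. They do not supply a reason for dropping vital signs and ECG, which the SAP itself lists and the protocol commits to describing.

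A reader might also infer more than the documents support:

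- *That the report will contain nothing but AEs and laboratory data.* SAP Sections 5 to 7 and 9 also plan disposition, Stage 2a exposure, demographics and PK. The gap is in the safety measures.
- *That the ten measure-by-stage items outside SAP 3.3 (3 + 7) were never planned.* Versions 1.0 and 2.0 are not available, so only their absence from version 3.0 can be shown.
- *That the protocol promises report tables when it says of the rat respiratory effects that "because the effects observed in this study were present at all doses, they will still be monitored closely in this clinical study".* This concerns monitoring during the trial, which scheduled assessments and the planned cohort reviews by the DMC and FDA can meet. The commitment to summaries comes from 9.4.2.3 to 9.4.2.5 alone. Equally, those reviews do not put group results in the CSR.
- *That the cut hides a safety signal.* Nothing in the documents suggests this.

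**Conclusion.** The point holds, and the SAP should be amended. Of the primary safety and tolerability measures, 2 of 7 in Stage 1 and 2 of 11 in Stage 2a are analysed. The clearest part is vital signs and ECG in both stages: listed in SAP 3.3, cut by SAP 3.5, and covered by explicit commitments in the protocol. The other measures (3 in Stage 1, 7 in Stage 2a) rest on the general commitment in protocol 9.4.2.5, so the case for full tables is weaker there.

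The fault is a missing measure-level justification together with unreported primary-objective data. It is neither concealment nor bias in an estimate. The conclusion rests on the public text of SAP version 3.0; pages removed from it were not seen. It also assumes that Stage 1 was completed. The SAP states completion of Stage 2a and of Cohort 6, but completion of Cohort 3, which could run in parallel with Cohort 4, is inferred.

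**What to change.** 1. Amend SAP 3.5 to keep endpoints 1 to 4 of SAP 3.3 for Stages 1 and 2a. Add vital-sign and ECG sections to SAP 8: baseline and change from baseline by timepoint, by dose, with vehicle pooled within stage as in SAP 4.0.
2. Provide at least listings for tolerability and drop comfort and for the ocular safety examinations.
3. Have Table 3 name each measure that is still dropped, or reduced to a listing, with its own reason. Record there that pooled-vehicle columns replace the protocol's layout by cohort and intervention. Reconcile SAP 3.5 and Table 3 with the PK analyses in Section 9.
4. If PCS criteria for vital signs or ECG were set in an earlier SAP version, restore them to Appendix B. If not, label any PCS counts post hoc.

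The cost is a longer synoptic CSR. Protocol 9.4.2.3 names 6 vital-sign parameters and 9.4.2.4 names 5 ECG parameters, so item 1 adds up to (6 + 5) × 2 stages = 22 parameter blocks, each repeated by timepoint. Each block has 4 columns (3 doses and pooled vehicle), against 3 × 2 + 1 = 7 in the protocol's layout. The number of timepoints cannot be read from the public schedules. No new data or visits are needed.

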9.6. Data Monitoring Committee (DMC)

An internal independent review team (comprised of but not limited to, a medical safety physician, statistician, clinical pharmacologist, and a clinical representative) will make up the DMC for the study. The composition of the independent team will be documented in the DMC Charter, TMF, and clinical study report. The members of the independent team will be different from the study team members who manage and maintain the study conduct activities, including data collection, data clarification, analysis development, safety monitoring, study center monitoring and management. The DMC will convene after the conclusion of each cohort in Stages 1 and 2a and conduct a comprehensive review of unmasked study data to recommend to either proceed to the next cohort(s), stop the next cohort(s), or modify the dose level or sample size of the next cohort(s). In addition, the FDA will review study data after the completion of each cohort and the sponsor will wait until a positive response is received from the FDA to proceed to the next cohort. Following the completion of Cohort 6 (Stage 2a), the DMC will review unmasked safety, exposure, and exploratory efficacy data to recommend dose selection for Stage 2b or additional dose strength to investigate.

All details of the committee membership, procedures for safety review, frequency of review and communication between the safety review committee and other information will be detailed in the DMC charter.

10. Supporting Documentation and Operational Considerations

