12.1 Changes to Planned Analyses in the Protocol

Due to the early discontinuation of the study after completion of Cohort 6, there will not be any subjects in Stage 2b, hence no Stage 2b related analysis will be conducted.

Changes from the originally planned statistical analysis specified in the protocol are outlined Table 3.

Table 3. Changes to Planned Analyses in the Protocol

Statistical Analysis Plan	Rationale for Changes

 No statistical analysis or outputs to be generated for Stage 2b or other objectives/endpoints Synoptic CSR will be provided. Only key safety analysis will be performed. 	Early study termination prior to Stage 2b

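### SAP version 3.0 analyses no Stage 2a efficacy endpoint, although Stage 2a was completed, and neither reason it gives explains why

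*SAP*

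**What the plan says.** **The objective and the planned analysis.** Protocol Section 3 lists as a Stage 2a objective, in the secondary block: "To evaluate efficacy of AGN-241622 compared with vehicle after repeat bilateral administration in participants with presbyopia". Protocol Section 9.4.1 places the Stage 2 efficacy analyses in the ITT population. Section 9.4.1.2 plans frequency tables by dose for the 3-line responder endpoint at Day 14, Hour 3, with missing data counted as nonresponse. Section 9.4.1.3 plans frequency and summary tables for the other endpoints without imputation.

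**What the SAP still lists.** SAP Section 2.1 says: "The primary objective of this study is to evaluate the safety, tolerability, pharmacokinetics, and efficacy of AGN-241622". SAP Section 3.1 says: "The primary efficacy endpoint is the proportion of subjects gaining 3 lines or more from baseline in mesopic, high-contrast, binocular DCNVA", assessed at Day 14, Hour 3. SAP Section 3.2 lists nine further efficacy endpoints. Neither list is marked as not analysed.

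**What the SAP will analyse.** SAP Section 3.5 says that "only the endpoints 1 and 4 of Section 3.3 Safety Endpoints will be analyzed". Table 3 in SAP Section 12.1 declares that there will be no outputs for Stage 2b or for other objectives and endpoints, and that only key safety analysis will be done.

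**Status and reasons.** SAP Section 1.0 says "the study was terminated after Stage 2a completion", by sponsor decision and not for safety. The footnote to SAP Table 1 says "Stage 2b has not been conducted due to early discontinuation of the study after completion of Cohort 6". The rationale cell of Table 3 reads: "Early study termination prior to Stage 2b". SAP Section 3.5 and the version history add the change to a synoptic report.

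**The concern.** A stage that was run to completion had a stated efficacy objective and a specified table to address it. The SAP that governs the report keeps the endpoint definitions but plans no output from them. The reason in Table 3 fits Stage 2b, which enrolled nobody, and does not fit Cohorts 4 to 6, whose Day 14 assessments do not depend on Stage 2b.

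Stage 1 had no efficacy measures (Protocol Section 8.1), and Cohort 8, the only other vehicle-controlled cohort with efficacy measures, was not run. Stage 2a is therefore this trial's only vehicle-controlled efficacy information, on a compound that had no earlier clinical experience (Protocol Section 2.3). Under the current SAP, the report would not describe near-vision response at any dose, and a reader could not tell from the SAP why.

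**Working it through.** **1. Planned size of Stage 2a.** Inputs: three cohorts, each with 9 active and 3 vehicle (Protocol Table 4-1, SAP Table 1).

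- Total: 3 × (9 + 3) = 36, which reproduces the 36 in Protocol Appendix 6.
- Active: 3 × 9 = 27, or 9 per dose if each cohort tested one distinct dose.
- Vehicle: 3 × 3 = 9, pooled within Stage 2a under SAP Section 4.0.

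**2. Efficacy endpoints with Stage 2a data.**

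- SAP Section 3.1: 1. SAP Section 3.2: 9. Sum: 1 + 9 = 10.
- Item 5 of Section 3.2 (DCIVA) is measured only in Stage 2b (Protocol Section 8.1), so 10 − 1 = 9.
- Number analysed under SAP Section 3.5: 0 of 9.

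**3. Do the stated reasons reach Stage 2a?**

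| Stated reason | Where | What it explains |
|---|---|---|
| Termination before Stage 2b | SAP Section 12.1, text and Table 3 | No Stage 2b analysis. It does not reach Cohorts 4 to 6, which were complete. |
| Change to a synoptic report | SAP Section 3.5 and version history | A shorter report. It is a choice of format and does not say why a short descriptive table must be left out. |

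The second reason applies beyond Stage 2b, so it would be wrong to say that the SAP's reasons concern Stage 2b alone. It still does not explain why this objective was dropped. SAP Section 9.0 keeps descriptive PK summaries for Stages 1 and 2a. These also fall outside endpoints 1 and 4, so the reduced scope is not applied consistently within the SAP.

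**4. Can the SAP as written produce the tables?** No. It has safety and PK analysis sections but no efficacy analysis section in the text available, and Section 4.0 assigns the ITT population to baseline analyses. Editing Section 3.5 alone would not be enough.

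**5. How much would the restored table tell?** The documents give no responder rates, so the counts below are assumptions across the possible range. The exact (Clopper-Pearson) 95% interval for x of n has as its lower limit the 2.5% quantile of Beta(x, n − x + 1), and as its upper limit the 97.5% quantile of Beta(x + 1, n − x). When x = 0 the lower limit is 0 and the upper limit is 1 − 0.025^(1/n). For n = 9 that upper limit is 1 − 0.025^(1/9) = 0.336.

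| Responders of 9 | Exact 95% interval |
|---|---|
| 0 | 0 to 33.6% |
| 1 | 0.3 to 48.3% |
| 3 | 7.5 to 70.1% |
| 5 | 21.2 to 86.3% |
| 9 | 66.4 to 100% |

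The intervals are wide. The table would describe the response in each group and would rarely settle whether a dose works.

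**The case against.** The case for leaving the SAP as it is has real substance.

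- **The cut is declared.** SAP Section 3.5 and Table 3 say openly that other endpoints will not be analysed. This stands: the fault is an inadequate reason and endpoint lists left unmarked, not concealment.
- **Efficacy is not the primary objective of Stage 2a.** The protocol puts safety first, tests no hypotheses (Section 9.1), gives no statistical basis for sample size (Section 9.2) and expects only a numeric improvement in DCNVA over vehicle (Section 4.1.1). SAP Section 2.1 is a one-sentence summary of the whole study and should not be read as raising efficacy to a Stage 2a primary objective. This stands, and it limits the size of the loss. It does not remove the point, because the protocol planned descriptive tables knowing that the groups were small.
- **A terminated programme may reasonably report less.** This is fair as a general matter, but the SAP should then say so for Stage 2a.

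A reader might go further and infer selective non-reporting: that efficacy was dropped because the results had been seen. Protocol Section 9.6 does plan that after Cohort 6 "the DMC will review unmasked safety, exposure, and exploratory efficacy data to recommend dose selection for Stage 2b", and SAP version 3.0 was prompted by the discontinuation that followed completion of Cohort 6. The documents do not support the inference. SAP Section 10.1 makes efficacy review conditional on need, and nothing states that the DMC saw efficacy data. DMC members are separate from the study team, including those who develop the analyses. The same sentence in SAP Section 3.5 also drops vital signs and ECG, which suggests a broad reduction, not one aimed at efficacy. The text of SAP version 2.0 is not available, so it cannot be said which version removed the efficacy analyses.

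**Conclusion.** The point holds as a gap in reporting and justification. SAP version 3.0 analyses 0 of the 9 listed efficacy endpoints that have Stage 2a data, so a secondary objective of a completed stage gets no result. Neither stated reason accounts for that. What is lost is a descriptive comparison of three dose groups with pooled vehicle, planned at 9 participants each; it is not a confirmatory test. The documents do not show that results influenced the decision, and this point does not claim it.

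The verdict assumes that the planned numbers were roughly achieved (actual Stage 2a enrolment is not in the documents), that each of Cohorts 4 to 6 tested a different dose (strengths are redacted and the DMC could recommend repeating one), and that the Day 14, Hour 3 assessments were collected as planned.

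**What to change.** In SAP Section 3.5 and Table 3, restore for Cohorts 4 to 6 at least the Section 3.1 responder table at Day 14, Hour 3. Present it for each dose and for pooled vehicle in the ITT population, with counts, percentages and exact 95% intervals, and with missing data counted as nonresponse as in Protocol Section 9.4.1.2. Preferably also restore descriptive summaries of Section 3.2 items 1 to 4 and 6 to 9 on observed data, as in Protocol Section 9.4.1.3.

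To make these analyses runnable:

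- Add a short efficacy analysis section.
- Extend the use of the ITT population in SAP Section 4.0 to efficacy.
- Mark Section 3.2 item 5 (DCIVA) as not analysed, since it belongs to Stage 2b only.
- If the questionnaire items are restored, state or cite the NVPTQ and PICQ scoring rules. The available text does not give them, and the protocol refers details to the study procedure manual.

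The cost is SAP wording, a few extra tables from assessments the protocol already scheduled, and a slightly longer synoptic report. No new participants or visits are needed.

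If the sponsor still declines, mark SAP Sections 3.1 and 3.2 as not analysed and give in Table 3 a reason specific to Stage 2a. That entry should state whether the decision came before or after any unmasked review of efficacy data, without presuming that such a review took place.
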